8.2 Analyses

Analyses Population

Analysis of primary and secondary efficacy variables will be based on the response-evaluable population, which includes all subjects who have measurable disease and received at least 2 cycles of study treatment, and have at least 2 efficacy evaluation assessments. All safety analyses for AEs will be based on the safety analysis set, which includes all subjects who receive at least 1 cycle of study treatment.

Safety Analysis

The study will begin with accrual of 6 patients in a safety run-in with interim safety analysis occurring after these 6 patients have completed at minimum Cycle 1 and further accrual stopped until safety analysis completed. If $\geq 2/6$ patients in the safety cohort have dose limiting toxicities (DLTs) as defined in [Section 5.4](#), then further study accrual will be halted until the study PI, co-investigators, and the DSMC can review the data, and determine whether the study should continue, be amended with a lower starting dose of azacitidine, or be closed to further accrual. Toxicities will be monitored throughout the study using CTCAE 5.0 criteria. Though we do not expect to observe DLTs during the study period, formal safety bounds based upon monitoring DLTs as defined in [Section 5.4](#) will guide decisions about early stopping due to potential safety concerns. A Pocock-type sequential boundary⁵⁹ will be used to monitor dose-limiting toxicities with the aim of keeping the probability of early stopping at around 90% if the true underlying toxicity rate is 25%. If the number of dose-limiting toxicities is equal to or exceeds the stopping boundaries detailed in the following table at any point in the study, then accrual to the study will be suspended until the study PI, co-investigators, and the DSMC can review the data, and determine whether the study should continue, be amended with a lower starting dose of azacitidine, or be closed to further accrual. With a toxicity rate of 25%, the expected number of enrolled patients before stopping for excessive toxicities is 6.5.

Table 8-1. Table: Safety monitoring bounds for DLTs

Number of subjects	Stopping boundary
6-9	≥ 2
10-14	≥ 3
15-18	≥ 4
19-23	≥ 5

Adverse Events

Adverse events for safety analysis will be monitored for the duration of patient's treatment until 30 days post completion of treatment. The verbatim terms used in the CRF by investigators to identify adverse events will be coded using the Medical Dictionary for Regulatory Activities (MedDRA). Treatment-emergent adverse events are adverse events with onset during the induction/consolidation or maintenance treatment phase or that are a consequence of a pre-existing condition that has worsened since baseline. All reported adverse events will be included in the analysis. For each adverse event, the percentage of subjects who experience at least 1 occurrence of the given event will be summarized.

Summaries, listings, datasets, or subject narratives may be provided, as appropriate, for those subjects who die, who discontinue treatment due to an adverse event, or who experience a severe or a serious adverse event. These will be provided using the same formats as those used for adverse events. At study conclusion frequency, proportion and severity of adverse events, and DLTs by dose level will be tabulated. Point estimates and confidence intervals will be calculated for all dichotomous endpoints.

Efficacy Analysis

Response to study treatment and progressive disease will be evaluated by the IMWG response criteria.⁵⁵

Primary endpoints for efficacy

Primary endpoints for efficacy will be assessed by ORR. See [Section 2.3](#) for definitions. To account for the adaptive nature of Simon's two-stage design, we will calculate the uniformly minimum-variance unbiased estimator, p-value and 95% CI for the response rates. The calculation will be performed using R *clinfun* package (www.r-project.org).

Secondary endpoints for efficacy

Secondary endpoints for efficacy will be assessed using duration of response (DOR), progression-free survival (PFS), and overall survival (OS). DOR is defined as the duration from the date of initial documentation of a response (PR or better) according to the IMWG criteria to the date of first documented evidence of progressive disease according to the IMWG criteria or death due to PD whichever occurred first. DOR for subjects who have not progressed will be censored at the last disease evaluation before the start of any subsequent anti-myeloma therapy. PFS which is defined as the duration from the date of first dose of study treatment to the date of first documented evidence of progressive disease or death, whichever occurs first. Participants without a disease assessment will be censored at the date of first study treatment received. OS will be calculated as the time from the first dose of study treatment until death from any cause. Participants who have not died will be censored at the last time the participant was known to be alive. Distributions of DOR, PFS, and OS will be summarized using the Kaplan-Meier estimator. For each secondary efficacy endpoint, median even-free survival will be reported and the corresponding 95% confidence interval will be calculated using Brookmeyer and Crowley method.

Correlative Studies Analysis

CD38 regulation by azacitidine (Secondary Endpoint)

Change in CD38 surface expression in MM patients treated with azacitidine will be summarized using descriptive statistics and tested using the one-sample t-test. Two-sided p-value less than 0.05 will be considered statistically significant. The proportion of patients with at least a 1.5 fold increase in CD38 expression after one cycle of azacitidine treatment will also be reported. This phase II sample size of 23 will provide >99% statistical power to detect a fold change of 1.965 (SD: 0.299) in CD38 surface expression of MM patients treated with azacitidine based on a one-sample t-test at a two-sided type I error rate of 0.05. This estimated change in CD38 surface expression was calculated from our preliminary pre-clinical data. The association between the fold change in CD38 expression post azacitidine treatment and depth of response and duration of response will also be evaluated using logistic regression, linear regression methods, and Spearman's correlation coefficient, as appropriate.

DNA methylation pattern changes with azacitidine (Exploratory Objective, contingent upon funding)

Paired t-tests will be used to compare the DNA methylation levels between the samples pre and post Aza treatment. Analysis will be corrected for multiple hypothesis testing by controlling the false discovery rate (FDR). The distribution of uncorrected p values will be analyzed and an FDR will be inferred for each differentially methylated region (DMR). The inference will be made using the q value method available in R/Bioconductor. The dependence between statistical tests carried out for neighboring CpGs will be modeled to increase statistical power. Statistical comparisons will be carried out on larger genomic regions rather than single CpGs, such that neighbouring CpGs with similar differences in DNA methylation reinforce each other and give rise to more significant results. Hierarchical models will be used to minimize small standard deviations that frequently arise by chance. Standard deviation of a given CpG or genomic region will be estimated as the average of observed and expected values to obtain more robust P values for DNA methylation comparisons. A ranked list of DMRs will be established by incorporating p values as well as the relative and absolute differences in DNA methylation between samples pre and post Aza treatment.

Assessment of bone marrow tumor microenvironment changes (Exploratory Objective, contingent upon funding)

CyTOF will be used to report the changes in bone marrow tumor microenvironment before and after treatment with Aza, one of the exploratory endpoints of the study. Data generation and analysis will be done in collaboration with [name] laboratory at UCSF.

Data normalization and gating

After acquisition, data from acquired samples will be bead-normalized using MATLAB-based software. Barcoded cells will be assigned back to their initial samples using MATLAB-based debarcoding software. Normalized data will be then uploaded onto the Cytobank analysis platform to perform initial gating and population identification using the indicated gating schemes.

Data visualization and analysis

For further downstream analysis, pre-gated data will be imported into the R environment using the flowCore package. Data will be transformed with an inverse hyperbolic sine (arcsinh) transformation using a cofactor of 5 and normalized to the 99.5th percentile of each respective channel before downstream tSNE and Scaffold analysis. Visualization of samples by tSNE dimensionality reduction will be calculated using the Rtnse package with default parameters: perplexity = 30, theta = 0.5, max_iter = 1000 using the indicated

channels. To build a reference scaffold, bead and percentile-normalized data from live, CD45+, single, non-neutrophil cells will be imported into the statisticalScaffold package. All available channels will be used to build the reference maps. All population-relevant antigens will be included in the clustering analysis. Astrolabe analysis will be carried out by uploading bead-normalized data. Single-cell data will be clustered using the FlowSOM R package. Cell subset definitions follow. Cluster labeling method implementation, and visualization will be done through the Astrolabe Cytometry Platform (Astrolabe Diagnostics, Inc.).

Statistical analysis

In order to identify parameters of the immune system that are impacted by azacitidine treatment, we will use unbiased, unsupervised approaches that have been developed from mass cytometry (CyTOF) data. We will utilize an unsupervised clustering algorithm to identify immune cell subsets that is capable of handling large datasets and has been utilized previously for this purpose (clara, implemented in R, as in Spitzer et al.³). Changes in the abundance of each cluster will be evaluated using permutation-based statistical methods adapted previously for this purpose (SAM, implemented in R, as in Bruggner et al.,⁴ Gaudilliere et al.,⁵ Spitzer et al.⁶), which accommodate paired data (before and after) and handle multiple hypothesis testing. Immune cell subsets will be considered to change significantly when $q \leq 0.05$. We will evaluate both changes in immune cell abundances as well as changes in immune cell proliferation (% Ki-67+ cells) in this way. We will further evaluate significant results by manually identifying cell populations in the raw data by gating. These results will form the basis for the evaluation of a validation cohort in the future.

Visualization

Plots will be created using the ggplot2 R package. Schematic representations will be created with biorender (<https://biorender.com/>). Figures will be prepared in Illustrator (Adobe).

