Azacitidine will be given subcutaneously or IV at standard dose 75 mg/m^2 for 5 days consecutively every 4 weeks starting day -7 to day -3 of Cycle 1 (before first dose of daratumumab). The starting dose regimen of 75 mg/m^2 is based on prior trials leading to azacitidine approval in MDS and AML, including the azacitidine-001²⁸ and CALGB 8421, 8921, and 9221 trials.^{30,31} The dosing of azacitidine for 5 days consecutively (instead of 7) will be used for both patient convenience and to minimize toxicity. This is based on a study that showed that 5 days of consecutive azacitidine had similar efficacy to 7 days.³⁹ Azacitidine prescribing information created by Celgene suggests dose adjustments for azacitidine based on hematologic toxicity and our dose de-escalation follows these recommendations.⁵⁰ Dexamethasone 40 mg will be given orally once weekly on days 1, 8, 15, and 22 of each four-week cycle starting day 1 of cycle 1 for at least the first two cycles. Dose modifications for azacitidine and dexamethasone based on toxicities are outlined in [Section 5.5](#). There will be no dose modification for daratumumab. Treatment will be continued until progression or patient unable to tolerate treatment due to toxicities.

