2.3 Primary, Secondary, and Exploratory Endpoint(s)

Primary endpoints:

- Rate of overall response (ORR) defined as sCR+CR+VGPR + PR as best response utilizing IMWG Uniform Response Criteria⁵⁵ calculated in the time period from initiation of study treatment until discontinuation of treatment

Secondary Endpoints:

[figure not shown]
- Adverse events, as graded by National Cancer Institute Common Terminology Criteria for Adverse Events (NCI CTCAE version 5.0), assessed from the initiation of study treatment until discontinuation of treatment
- Duration of response (DOR) defined as the duration from the date of initial documentation of a response (PR or better) according to the IMWG criteria to the date of first documented evidence of progressive disease according to the IMWG criteria or death due to PD whichever occurred first.
- Overall survival which is defined from the date of first dose of study treatment to the date of death due to any cause or censored based on the date of last encounter if patient is alive or lost to follow-up.
- Progression-free survival which is defined as the duration from the date of first dose of study treatment to the date of first documented evidence of progressive disease or death, whichever occurs first.
- Change in CD38 surface expression of plasma cells after azacitidine treatment (the CD38 expression of plasma cells pre and post first cycle of azacitidine treatment in this trial will be compared)
- Number of patients who achieve at least 1.5 fold increase in their CD38 expression by flow cytometry after azacitidine treatment
- Correlation of change in CD38 expression after azacitidine treatment to response including depth of response and duration of response

3 Study Design

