6.1 Study Calendar

Period/ Procedure	Screening	Cycle 1 ^a (Pre- Induction Phase)	Cycle 1-2 ^a (Induction Phase)				Cycle 3 ^a (Consolidation Phase)				Cycle 4 ^a (Consolidation Phase)				Cycle 5-6 ^a (Consolidation Phase)				Cycle 7 ^a and Onwards (Maintenance Phase)	End of Treatment	Follow-up ^t	
Study Day/Visit Day	D -27 to D-8	D -7 to D-3	D1 (± 1 day)	D8 (± 1 day)	D15 (± 1 day)	D22 (± 1 day)	D1 (± 2 days)	D8 (± 2 days)	D15 (± 2 days)	D22 (± 2 days)	D1 (± 2 days)	D8 (± 2 days)	D15 (± 2 days)	D22 (± 2 days)	D1 (± 2 days)	D8 (± 2 days)	D15 (± 2 days)	D22 (± 2 days)	D1 (± 3 days)			
Study Treatment/Drug																						
Daratumumab ^b			x	x	x	x	x	x	x	x	x	x	x	x	x	x	x	x	x			
Azacitidine ^c		x				x			x				x		x		x		x			
Dexamethasone ^d			x	x	x	x	x	x	x	x	x	x	x	x	x	x	x	x	x			
Administrative Procedures																						
Informed Consent	x																			x		
Clinical Evaluation																						
Physical Exam	x	x	x				x				x				x				x			
Medical History	x																					
Vital signs	x	x	x	x	x	x	x	x	x	x	x	x	x	x	x	x	x	x	x	x		
Weight/height ^e	x	x	x	x	x	x	x	x	x	x	x	x	x	x	x	x	x	x	x	x		
Concomitant medications	x																					
AE assessment ^f	x																					
Performance status ^g	x	x	x				x				x				x				x			
Laboratory Assessments																						
Pregnancy Test ^h	x		x				x				x				x				x	x		
Type and Screen ⁱ	x																					
Hepatitis B (HBV) Serology ^j	x																					
HBV DNA Testing ^k	x																		x	x		
Blood	x	x	x	x	x	x	x	x	x	x	x	x	x	x	x	x	x	x	x	x		

Chemistry ^l																				
Hematology ^m	x	x	x	x	x	x	x		x	x	x		x	x	x	x	x	x	x	
Disease Evaluation^m																				
Immunoglobulin _{sⁿ}	x	x	x				x				x			x				x		
Serum M protein ^o	x	x	x				x				x			x				x		
sFLC ^p	x	x	x				x				x			x				x		
serum IFE ^q	x	x	x				x				x			x				x		
Urine M protein (24 hour urine) ^r	x																	x		
Skeletal Survey	Only as clinically indicated by standard of care																			
PET/CT/MRI	Only as clinically indicated by standard of care																			
Study Procedure/Correlative Studies																				
Bone Marrow Biopsy ^s	x		x																	

^a **Cycle:** Every cycle is 28 days (except for Cycle 1 which extends from day -7 to day 28). The treatment window is \pm 1 days for induction phase, \pm 2 days for consolidation phase, \pm 3 days for maintenance phase

^b **Daratumumab:** Daratumumab dose scheduling, pre-medications, dose modification, and DLTs are detailed in Section 5.

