8.1 Sample Size Determination

This is a single-arm, open-label, 2-stage phase II study designed to evaluate the efficacy of daratumumab in combination with azacitidine and dexamethasone in RRMM patients previously treated with daratumumab. A Simon's two-stage design⁵⁸ will be used for this study. The study will begin with accrual of 6 patients in a safety run-in. Safety monitoring bounds for study termination based on DLTs are described in [Section 8.2.2](#). If the safety stopping bounds are not met, study will continue to accrue more Stage I patients.

Sample size calculation was based on assessing the overall response rate (ORR) using Simon's minimax 2-stage design. Interim analysis for efficacy, using ORR, will be performed when the last patient enrolled to Stage 1 has received at least 2 cycles of treatment.

The overall target sample size of 23 patients is based upon having sufficient information to assess whether combined treatment of daratumumab with azacitidine and dexamethasone increases the ORR in this study population of RRMM patients with prior treatment with daratumumab. Data from ongoing clinical trial evaluating the safety, pharmacokinetics, and efficacy of isatuximab in patients with RRMM previously treated with daratumumab has shown preliminary results of ORR 8% (NCT02514668). Isatuximab is another CD38 monoclonal antibody with similar efficacy to daratumumab in RRMM patients.²⁴ Based on these previous results, for this study we would be interested in detecting an improvement in the ORR from a null rate of 8% to 33% ORR, which is based on the daratumumab-pomalidomide-dexamethasone

combination study in patients with RRMM re-treated with daratumumab.²³ Simon's minimax two-stage design will be used. The null hypothesis that the true response rate is 8% will be tested against a one-sided alternative that the true response rate is higher than 33%. In the first stage, 13 patients will be accrued. If there are 1 or fewer responses in these 13 patients, the study will be stopped. Otherwise, 10 additional patients will be accrued for a total of 23. The null hypothesis will be rejected if 5 or more responses are observed in 23 patients. The design will have a 90% power to reject the null hypothesis, if the true response rate is 33%, at one-sided 5% significance level. Accounting for an approximate 10% drop-out/ineligibility rate, maximum target accrual should not exceed 25 participants.

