8.3 Interim Analyses and Study Stopping Rules

As described in [Section 8.2.2](#), interim analysis will occur after accrual of 6 patients in the safety lead-in. Study accrual will be stopped until these 6 patients have completed at minimum cycle 1 of treatment, at which point a formal interim safety analysis will be performed with assessment for DLTs as defined in [Section 5.4](#) and safety stopping bounds for DLTs as described in [Section 8.2.2](#) and included again in the table below. If $\geq 2/6$ patients have DLTs, then further accrual to the study will be suspended until the study PI, co-investigators, and the DSMC can review the data, and determine whether the study should continue, be amended with a lower starting dose of azacitidine, or be closed for further accrual. Otherwise, study will continue. Safety monitoring will continue for the remaining duration of the trial. A Pocock-type sequential boundary⁵⁹ will be used to monitor dose-limiting toxicities with the aim of keeping the probability of early stopping at around 90% if the true underlying toxicity rate is 25%. The accrual will be halted until further study investigation if excessive numbers of dose-limiting toxicities are observed, that is, if the number of dose-limiting toxicities is equal to or exceeds the stopping boundaries in the following table. With a toxicity rate of 25%, the expected number of enrolled patients before stopping for excessive toxicities is 6.5.

Table: Safety monitoring bounds for DLTs

Number of subjects	Stopping boundary
6-9	≥ 2
10-14	≥ 3
15-18	≥ 4
19-23	≥ 5

As described previously in [Section 8.1](#), interim efficacy analysis will occur after completion of Simon's Stage I. 13 patients will be enrolled in Simon's Stage I. If there are 1 or fewer responses in these 13 patients, the study will be stopped. Otherwise, 10 additional patients will be accrued for a total of 23.

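### The primary ORR leaves early failures out of its denominator, so it is biased upward and does not match the accrued-patient 13/23 rules

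*Combined protocol and SAP*

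**What the plan says.** Section 8.2 (Analyses Population) restricts primary and secondary efficacy analyses to a response-evaluable population: "all subjects who have measurable disease and received at least 2 cycles of study treatment, and have at least 2 efficacy evaluation assessments".

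The decision rules are written on a different unit. Section 8.1 accrues 13 patients, stops at 1 or fewer responses, otherwise accrues 10 more, and then: "The null hypothesis will be rejected if 5 or more responses are observed in 23 patients". Section 8.3 repeats that "13 patients will be enrolled in Simon's Stage I". The Stage 1 look takes place "when the last patient enrolled to Stage 1 has received at least 2 cycles of treatment". After an allowance of about 10% for drop-out or ineligibility, "maximum target accrual should not exceed 25 participants".

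Section 2.3 defines the ORR without any two-cycle condition, as best response "calculated in the time period from initiation of study treatment until discontinuation of treatment". Section 7.1 (Response Categories) requires two consecutive assessments for every response category.

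No section counts early failures as non-responders, says who is replaced, or says what happens if fewer than 23 patients are evaluable.

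**The concern.** Membership of the primary set is decided by what happens after the first dose. A patient who progresses, dies or stops for toxicity in the first weeks has failed treatment, yet is removed from the analysis. Because response needs two consecutive assessments, those removed are nearly all non-responders. A few could be responders, since disease evaluations continue after stopping (Section 6.1 footnote t; Section 7.1).

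The unbiased estimate, p-value and 95% CI planned in Section 8.2 (Efficacy Analysis) would then describe patients who got through two cycles, while the comparison with 8% would be read as a result for treated patients. The Stage 1 decision could also be affected, depending on whether 13 means accrued or evaluable patients.

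Section 8.2 is not consistent with itself here. It gives a PFS censoring rule for participants with no disease assessment, although the population definition has already excluded them.

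**Working it through.** **Inputs.** Section 8.1: null rate 0.08, target rate 0.33, stop at ≤1/13, reject at ≥5/23, cap 25. Section 6.1 footnote a: Cycle 1 runs from day −7 to day 28, later cycles last 28 days. Abstract: about 8 months of treatment expected. Section 1.3: median PFS 3.5 months on the first regimen after relapse following a CD38 antibody. The excluded share d is not given, so 10% and 20% are assumed.

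**1. The plan's own figures.** P(reject) = Σ over x = 2 to 13 of P(X₁ = x | 13, p) × P(X₂ ≥ 5 − x | 10, p). At p = 0.08 this is 0.0302; at p = 0.33 it is 0.9031. The stated 5% level and 90% power reproduce. The chance of passing Stage 1, P(X ≥ 2 | 13, p), is 0.279 at 0.08 and 0.959 at 0.33.

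**2. How long a patient must stay.** Cycle 1 ends 7 + 28 = 35 days after first azacitidine, and Cycle 2 ends at 35 + 28 = 63 days. Entry to the set therefore needs roughly 35 to 63 days, depending on whether a cycle is received when started or when completed and whether baseline counts as an assessment.

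**3. Bias in the ORR.** If every excluded patient is a non-responder, the rate among evaluable patients is p/(1−d). If a share q of the excluded had responded, it is (p − dq)/(1−d).

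| True rate | d = 10%, q = 0 | d = 20%, q = 0 | d = 10%, q = 5% | d = 20%, q = 5% |
|---|---|---|---|---|
| 8% | 8.9% | 10.0% | 8.3% | 8.8% |
| 33% | 36.7% | 41.3% | 36.1% | 40.0% |

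In counts, 5 responders among 23 treated is 21.7%. With 2 excluded and not replaced it becomes 5/21 = 23.8%. With 25 treated and 2 excluded it is 5/23 = 21.7% instead of 5/25 = 20.0%.

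**4. Effect on the decisions, by reading of 13 and 23** (excluded patients all non-responders).
- *Accrued patients, as written:* excluded patients add no responses, so the decisions do not change. Stage 1 pass stays at 28% and type I error at 3.0%.
- *Evaluable patients, with 8% an all-treated rate:* Stage 1 pass at 0.08/(1−d) is 0.324 (d = 10%) or 0.379 (d = 20%). An exact recursion that stops at 23 evaluable or 25 enrolled gives type I error 0.0396 or 0.0431. It cannot exceed P(X ≥ 5 | 25, 0.08) = 0.0451.
- *Evaluable patients, with 8% an evaluable-patient rate:* Stage 1 pass is 0.279, and type I error under the cap is 0.0267 or 0.0185.

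**5. How large d might be.** Assume exponential exit and 30.44 days per month. For a median m, the share gone by day t is 1 − 0.5^(t/m). For a mean it is 1 − exp(−t/m). At days 35 and 63:
- 8 months of treatment as a median: 9.5% and 16.4%
- 8 months as a mean: 13.4% and 22.8%
- median PFS of 3.5 months: 20.4% and 33.6% progressed or dead

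**6. Does the cap cover the loss?** P(at least 23 evaluable of 25) is 0.537 at d = 10% and 0.098 at d = 20%.

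**The case against.** The 10% allowance, the cap of 25 and the two-cycle timing of the interim all fit an intention to have 13 and 23 *evaluable* patients. On that view the mismatch is an unstated intention rather than a contradiction. That is fair, but it would settle only the count. The ORR would still leave out early failures, and the cap often would not deliver 23 evaluable patients.

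On the literal accrued reading the go/no-go decisions do not move, and the Stage 1 inflation needs two conditions at once: 13 means evaluable, and 8% is an all-treated rate. This stands, and the Stage 1 figures should be read as conditional.

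The 3.5-month PFS comes from a refractory cohort. This trial excludes patients primary refractory to daratumumab and requires six months since the last dose. Progression is also not the same as exclusion: if starting Cycle 2 is enough, a patient who progresses during it can still qualify. So 20% to 34% is a rough guide that may overstate d. The protocol's 10% mixes drop-out with ineligibility and is not an early-failure rate either.

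At d = 10% the bias is at most 0.9 points at 8% and 3.7 points at 33%, small beside a single-stage exact 95% interval for 5/23 of about 7% to 44%. True, but the interval reflects chance, whereas this error always runs the same way and can be avoided.

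**Conclusion.** The concern holds. As written, the primary ORR excludes early failures and overstates the response rate among treated patients by a factor of up to 1/(1−d). The direction is clear; the size rests on an assumed d and on nearly all excluded patients being non-responders.

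The test level is intact under the written rejection rule and the 25-patient cap. A higher chance of passing Stage 1 with an inactive regimen (up to 32% or 38% against 28%) arises only if the 13 are evaluable patients and 8% is an all-treated rate. The documents do not give the denominator behind the 8%. If it is an evaluable-patient rate, the Stage 1 and type I effects disappear, but the overstatement of the ORR remains. This should be fixed before analysis.

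**What to change.** - Define the primary ORR population, at Stage 1 and at the end, as all patients with measurable disease who receive at least one dose of any study drug, including those who receive only the azacitidine given before Cycle 1 Day 1.
- Count as a non-responder anyone without a confirmed response, including patients who stop early or lack two assessments.
- Keep as a responder a patient whose response, first seen on treatment, is confirmed at an end-of-treatment or follow-up assessment before new therapy. Sections 2.3 and 7.1 should say that the confirming assessment may fall after treatment stops.
- Apply ≤1/13 and ≥5/23 to these patients in enrolment order.
- Run the interim when every Stage 1 patient has completed two cycles or stopped, and any first response seen by then has had its confirmatory assessment. No wait is needed once two responses are confirmed.
- Report the response-evaluable ORR as supportive, with the number excluded and the reasons.

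**Cost.** Wording, no added patients, and a less favourable ORR. Power stays at 90.3% if 33% is the all-treated rate. If 33% holds only among evaluable patients, the all-treated rate is 0.33 × (1−d) and power is 83.7% (d = 10%) or 74.2% (d = 20%), against 88.5% or 82.1% for the plan as written and capped at 25. Holding 90% in that case would need a larger sample.

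The interim may wait up to one more 28-day cycle. That wait protects power: if 20% of Stage 1 responses (an assumption) were still unconfirmed and counted as failures, the chance of passing Stage 1 at 33% would fall from 95.9% to 89.5%, and power from 90.3% to 85.2%.
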